BAILA Version #38; 6/6/2016 Unfortunately, Latinos aged 65-74 are 46% less likely to engage in leisure time PA than older non-Latino whites(5) and little is known about PA maintenance among ethnic minorities compared to non-Latino whites.(6) In part as a result of low levels of PA, the physical and cognitive function of older Latinos is poor relative to older non-Latino whites. Older Latinos are almost twice as likely to report difficulty walking than non-Latino whites and their use of assistive devices is 33% higher. (7-9) Moreover, the number of Latinos in the U.S. with Alzheimer's Disease (AD) is projected to increase by 600% in the next 50 years(10) and AD symptoms may begin seven years earlier in Latinos than in non-Latino whites.(11) Participation in PA has substantial potential to help older Latinos maintain both physical and cognitive function as they age. Walking and dancing are the two most commonly reported forms of PA among older Latinos. (12-15) However, urban older Latinos cite unsafe neighborhoods and extreme weather conditions as significant barriers to walking. Dance is a widely popular form of PA among Latinos of all ages(16, 17) and holds considerable promise as a culturally appropriate form of PA that challenges individuals both physically and cognitively. To date, PA programs designed for older Latinos are lacking. BAILAMOS© is an innovative dance program that has been developed by [name] (PI) based on focus group input from older community-dwelling Latinos and in collaboration with an accomplished Latin dance instructor. A single group, prepost 3-month pilot of BAILAMOS© demonstrated substantial program feasibility (only 3 of 12 participants dropped out, and participants attended 85% of the 24 sessions). Effect sizes (Cohen's d) indicated greater self-reported lifestyle PA (accumulation of leisure time, household, occupational, and transportation PA over the entire day)(18) (d=1.38) and greater enjoyment of PA (d=.61) following the intervention. Improvements in physical function (mobility, d=-.56; usual gait speed, d=-.10) and cognitive function (ds=.11-.12) were also seen. Now, a larger efficacy trial conducted over a longer time period is necessary to examine the intervention effects.

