The original 3-month BAILAMOS© dance program has been revised according to participant and dance instructor feedback. Eight sessions (1 month) have been added to increase overall dose of PA from 24 sessions over 3 months to 32 sessions over 4 months. Also, discussion sessions covering topics related to increasing lifestyle PA were added. We propose a randomized controlled trial (RCT) to test the efficacy of the revised 4-month BAILAMOS© program for improving lifestyle PA and health outcomes (physical and cognitive function, self-reported functional limitations, disability) in sedentary older Latinos at risk for disability relative to an attention control group. We will also test whether lifestyle PA and health outcomes can be maintained over an additional 4-months through BAILAMOS© maintenance activities, which include using indigenous dance leaders. This study will use an RCT (N=166 Treatment, 166 Control) with a health education control group that will allow us to examine the adoption of PA and its impact on health outcomes (first 4 months), and the short-term maintenance of PA and its impact on health outcomes (8 months) among older Latinos.

4. Methods

a. Research Design

A randomized controlled trial (RCT) followed by a debriefing session. Participants will: (a) testing at 0, 4, 8 months and (b) take part in the dance intervention or health education condition.

b. Eligibility Criteria

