- After the initial 4-month program, testing will occur. After this POST-intervention testing (month 4), a \$10 cash gift will be provided, and participants will be asked to wear an accelerometer for 7 days. When that accelerometer is returned, participants will receive another \$10 cash gift.
- After the maintenance 4-month program for dancers, testing will occur for both participants from the dance group and the health education group. At this month 8 testing, a \$10 cash gift will be provided, and participants will be asked to wear an accelerometer for 7 days. When that accelerometer is returned, participants will receive another \$10 cash gift. Thus, a total of \$60 is possible.
- Through Amendment # 16, we would like to allow research participants in the maintenance component of the program to invite 1 or 2 family member(s) or friend(s) to come dance with them. Both of the sites which are in the maintenance phase of the program are struggling with attendance adherence.

The person our participant invites will not be involved with any of the study procedures, such as:

- No visits to the University of Illinois at Chicago for questionnaires (No data collected on them)
- No need to wear accelerometer
- Not eligible for lotteries
- Not eligible for compensation

In addition, in order to attend a dance session, the person will need to:

- Be 55 years or older
- Be able to speak English and/or Spanish
- Not be in the Health Education group of the study
- Be physically able to dance (no assistive devices permitted like canes, walkers, or wheelchairs)
- Sign a one-time waiver
- Sign-in at each class attended

The investigator may stop a person from participating in the dance sessions of the maintenance program if the person is at risk of injury, or if he/she is disruptive or inappropriate during any session.

Emergency Procedures for Study Participant

In the event of an emergency, staff responds quickly and calmly.

All emergencies are documented in the participant's file and if the project coordinator is not onsite, she is notified immediately by the Indigenous Leader (Participant Leader). The emergency is brought to the attention of the Principal Investigator by the Project Coordinator, so he is aware of the problem and can discuss how to prevent future emergencies. In addition, the Project Coordinator files an adverse report form with IRB

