- 1. Our Lady of Mount Carmel
- 2. West Town Satellite Senior Center
- 3. Pilsen Satellite Senior Center (Alivio Medical Center)
- 4. Kelvyn Park Satellite Senior Center
- 5. Villa Guadalupe Senior Services INC
- 6. Southwest Center
- 7. St. Agnes of Bohemia
- 8. West Suburban Senior Services
- 9. Catholic Charities of Archdiocese of Chicago, St Mary of Celle
- 10. Northwest Copernicus Regional Senior Center
- 11. Holy Cross Immaculate Heart of May Church
- 12. Mile Square Health Center—Recruitment ONLY
- 13. Dance Academy of Salsa

f. Statistical Methods

Aim 1. Hypothesis: Lifestyle PA (self-reported and accelerometer-assessed) will be significantly higher in the BAILAMOS© group at 4 and 8 months compared to the control group.

The proposed study uses a between-groups design with two groups and individual covariates. Initially, descriptive statistics will be obtained (e.g., for continuous variables we will examine means and standard deviations) and we will screen for wild codes (e.g., extreme values as the result of typos in data entry).

Using t-tests and chi-square tests, we will examine all baseline outcomes and covariates to determine whether randomization has produced equivalent groups. Variables exhibiting differences will be added as covariates to analyses. Transformations to achieve normality will be applied as needed; and residuals from analysis will be examined to detect multivariate outliers. Data will be examined for differential dropout but dropout is expected to be missing at random (MAR) and will thus not be imputed unless necessary.

Analysis will be carried out using standard mixed model analysis of variance and covariance using the SAS program (i.e., PROC MIXED), controlling for antecedent factors measured at

baseline including demographics, body composition, acculturation, and health status. For Aim 1 the Group x Time interaction term will test whether there is greater improvement in self-reported and accelerometer-assessed lifestyle PA at 4 and 8 months in the treatment group compared to the control group.

Aim 2. Hypothesis 2a: Self-efficacy for PA, Balance, and Gait will be significantly higher in the BAILAMOS© group at 4 and 8 months compared to the control group.

The same analysis strategy in Aim 1 will be applied for Aim 2, Hypothesis 2a. The Group x Time interaction term will test whether there is greater improvement in self-efficacy at 4 and 8 months in the treatment group compared to the control group.

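### The physical activity model has no site-cohort or calendar term, so seasonal change shared by both arms stays in the error of Group x Time: a modest loss of precision, not bias

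*Combined protocol and SAP*

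**What the plan says.** Section 4.f of the combined protocol and SAP describes the analysis at the level of the person: "The proposed study uses a between-groups design with two groups and individual covariates". Lifestyle PA, self-reported and by accelerometer, is analysed in PROC MIXED. The Group x Time interaction is the test, "controlling for antecedent factors measured at" "baseline including demographics, body composition, acculturation, and health status". One further rule can add covariates after baseline groups are compared: "Variables exhibiting differences will be added as covariates to analyses". Site, start cohort, class, season and visit date are not named in 4.f.

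Other sections give the setting:

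- Section 3 says that "urban older Latinos cite unsafe neighborhoods and extreme weather conditions as significant barriers to walking", and that walking and dancing are the commonest forms of PA in this population.
- Section 4.a sets testing at months 0, 4 and 8. Section 4.e makes the accelerometer outcome a 7-day reading at each visit.
- Section 4.e lists 13 sites, one of them for recruitment only, which leaves 12 for delivery. The Amendment 16 text says "Both of the sites which are in the maintenance phase of the program are struggling with attendance adherence", and the emergency procedures list only three current sites.
- Section 4.e assigns individuals to arms by software and states no stratification by site or cohort.

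**The concern.** A week of PA measured in a Chicago winter may differ from one measured in summer for reasons unrelated to the programme. If cohorts start in different months, each has its own seasonal change from month 0 to 4 and from 0 to 8, and both arms of the cohort share it. The Time effect removes only the average of these changes. The departures of each cohort from that average stay in the residual against which Group x Time is tested.

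Neither route to adjustment in 4.f brings season in. The covariate list covers factors measured at baseline, and the data-driven rule covers variables that differ between arms at baseline. Season at months 4 and 8 is neither. A participant-level random effect does not remove it either, because it is a change and not a stable level. What is at stake is precision on the Aim 1 outcomes, and a choice of adjustment left open until the data are seen.

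**Working it through.** **The plan's own figure.** The documents give 166 + 166 = 332 participants but no alpha, power, SD, between-group effect or dropout rate, so the sample size cannot be reproduced. As an assumption only (two-sided 0.05, 80% power, no dropout), 166 per arm corresponds to d = (1.960 + 0.842) x sqrt(2/166) = 0.308 SD. This value is used below.

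**Season of the visits.** For each of 365 start dates, under both meteorological and astronomical seasons, none puts months 0 and 4, 4 and 8, or 0 and 8 in the same season. The same holds for consecutive visits exactly 16 or 17 weeks apart.

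**Seasonal variance of a change score.** Assume a yearly cosine of amplitude a, in SDs of individual change, and starts spread evenly over the year. A 4-month gap is 120 degrees, so cos(x + 120°) − cos(x) has amplitude 2 sin 60° = 1.732. An 8-month gap (240 degrees) gives 2 sin 120° = 1.732. The variance between cohorts is therefore 1.732² a²/2 = 1.5a², against an individual variance of 1.

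- Share of total variance: s = 1.5a²/(1 + 1.5a²)
- Standard error ratio: 1/sqrt(1 − s) = sqrt(1 + 1.5a²)
- Effective loss out of 332: 332 x s
- Extra participants to offset it: 332 x s/(1 − s) = 332 x 1.5a²

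| a (assumed) | 1.5a² | s | SE ratio | Effective loss of 332 | Extra beyond 332 |
|---|---|---|---|---|---|
| 0.20 | 0.060 | 5.7% | 1.03 | 19 | 20 |
| 0.25 | 0.094 | 8.6% | 1.05 | 28 | 31 |
| 0.35 | 0.184 | 15.5% | 1.09 | 52 | 61 |

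These figures are before the cost of the added degrees of freedom. The documents give no PA variance or seasonal amplitude, so a is an assumption throughout.

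**Simulation of the change score.** Assumptions: 12 site-cohorts, random start month, individual randomisation, effect 0.308 SD, no class effect, 4,000 runs. Cohort change is seasonal (amplitude a) plus other cohort variation (SD t).

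| a, t | Allocation | Power without term | Power with term | Type I without term |
|---|---|---|---|---|
| 0, 0 | unstratified | 80.8% | 79.1% | 4.8% |
| 0.2, 0.1 | unstratified | 78.6% | 79.7% | 4.9% |
| 0.3, 0.2 | unstratified | 72.6% | 78.0% | 4.9% |
| 0.3, 0.2 | balanced within site | 74.2% | 79.0% | 3.7% |
| 0.5, 0.3 | balanced within site | 66.8% | 79.9% | 1.7% |

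The mean error of the Group x Time estimate was below 0.004 SD in every case. With unstratified allocation the test holds its level but the estimate is noisier. With balanced allocation the estimate is as precise as it can be, but the reported standard error is too large and the test is conservative. With season alone and a = 0.25 to 0.35, the term gained about 2 to 5 points of power. When starts fell in one season, or there was no swing, it lost up to about 1.5 points.

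**Interaction with class clustering.** Classes are specific to arm within site. With an assumed class ICC of 0.03, balanced allocation, a = 0.25 and no class effect in the model, type I error was about 8–9% without the cohort term and about 10% with it. At a = 0.35 it rose from 6.9% to 9.2%. The cohort term shrinks the residual but leaves the class variance in the arm contrast, so the understatement of the standard error becomes proportionally larger.

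**The case against.** The strongest reply is that this is an efficiency gain and not a flaw. Group x Time is a concurrent randomised comparison, and omitting the term leaves it unbiased, with type I error near 5% or below when classes are not clustered. That stands. A reader might infer that season confounds the comparison of the arms; the design and the simulation do not support this.

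A reader might also infer that maintenance from month 4 to 8 cannot be assessed because it is mixed with season. Section 3 does state the aim: "We will also test whether lifestyle PA and health outcomes can be maintained over an additional 4-months". But Hypothesis 1 in section 2 is worded against control at both times, and 4.f tests it by Group x Time. No within-arm maintenance test is planned, so this is not a defect of the plan.

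Four further limits stand:

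- The protocol speaks of significant barriers to walking, while the outcome is all lifestyle PA.
- Stable neighbourhood differences cancel in within-person change, so neighbourhood safety adds little to the case.
- The covariate list is introduced as examples, so a term is unspecified and not ruled out.
- Staggered starts are inferred. If cohorts start in similar months, the Time effect absorbs the common swing and the gain disappears.

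None of this removes the point that the plan, as written, supplies no route by which cohort-specific change would be adjusted for.

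**Conclusion.** The concern holds as one of precision and prespecification for the PA outcomes. Under starts spread over the year and an amplitude of 0.20 to 0.35 SD of change, the standard error is about 3% to 9% larger before the cost of degrees of freedom. The gain is about nil if cohorts start in the same season, and slightly negative if there is no seasonal swing. The size rests on assumed values, since the documents give neither a cohort calendar nor variances. Clustering by class is a separate and more serious gap: with about 14 per class (332/12/2) and an assumed ICC of 0.01 to 0.05, the design effect is 1.13 to 1.64. The cohort term does not repair that.

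**What to change.** In 4.f, for the self-reported and accelerometer PA models, prespecify site-by-start-cohort x visit as fixed effects common to both arms. Pair this with a random effect for class (arm within site-cohort), allowed to vary by visit so that it captures shared change and not only shared level. A cohort main effect alone would not do, because it leaves cohort-specific change in the error. State the cohort start dates and whether allocation was stratified by site.

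The cost is about two degrees of freedom per cohort (about 24 if each of the 12 delivery sites is one cohort) and up to about 1.5 points of power if there is no seasonal swing. The class effect may widen the standard error, but that reflects real clustering. No new procedure is needed provided that site, class and start cohort are on file, which is likely but not stated. The terms should be fixed before outcomes are compared by arm.

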Aim 2. Hypothesis 2a1: Self-efficacy for PA, Balance, and Gait will mediate the effect of the BAILAMOS© program on lifestyle PA and health outcomes.

In connection with Aim 2, Hypothesis 2a, we will conduct mediation analysis following testing procedures recommended by MacKinnon. We will examine whether self-efficacy is a necessary intervening variable to produce the PA and health outcome differences. We will use methods provided in the M-Plus statistical package, which offers special facilities for estimating standard errors of mediation terms.

Aim 2. Hypothesis 2b: Physical function, cognitive function, and self-reported functional limitations and disability scores will be significantly better in the BAILAMOS© group at 4 and 8 months compared to the control group.

Analysis will be the same as Aims 1 and 2. The Group x Time interaction term will test whether there is greater improvement in physical function, cognitive function, and self-reported functional limitations and disability scores at 4 and 8 months in the treatment group compared to the control group.

g. Safety Monitoring and Assessment

Risks:

The risk level of the intervention is minimal. For the proposed study there is the potential that undocumented Latinos will want to participate and will be concerned about anonymity and confidentiality in participating.

There is a small possibility that the older adults could injure themselves during the testing or the dance program.

Possible risks associated with physical injury that could occur during the dance intervention include those that one would experience with any physical activity, including (1) strains, sprains, muscle soreness, aggravation of arthritic conditions, etc. (2) slipping/tripping/falling; (3) bumping into another participant; (4) a very slim chance that cardiac irregularities can occur. This is very rare and the benefits of exercise are known to outweigh the risks. Serious physical injury or severe pain is considered unlikely. In our pilot test of the BAILAMOS© dance program, we had 12 participants, 9 of whom completed the 12 week program that took place two times per week. We experienced no serious injuries or falls.

The following provides steps that we will take to (1) address the potential for risks, and (2) handle injuries should they occur.

- 1) Addressing the potential for risks

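### The mediation plan for Hypothesis 2a1 does not specify baseline self-efficacy or the baseline outcome, so the self-efficacy-to-outcome path is left open to confounding

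*Combined protocol and SAP*

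**What the plan says.** Section 4.f, Hypothesis 2a1, states that self-efficacy for PA, balance and gait "will mediate the effect of the BAILAMOS© program on lifestyle PA and health outcomes". The method takes three sentences. The first cites published mediation testing procedures. The second sets the question: "We will examine whether self-efficacy is a necessary intervening variable to produce the PA and health outcome differences". The third names the software: "We will use methods provided in the M-Plus statistical package, which offers special facilities for estimating standard errors of mediation terms". There is no equation, no covariate, no mediator or outcome time, and no statement of whether follow-up levels or change scores are used.

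Baseline control appears earlier in section 4.f, under Aim 1. The PROC MIXED models control for factors measured at "baseline including demographics, body composition, acculturation, and health status". For Hypothesis 2a, "The same analysis strategy in Aim 1 will be applied for Aim 2, Hypothesis 2a", and a separate sentence carries the analysis to Hypothesis 2b. No such sentence covers 2a1. The Aim 1 list names neither baseline self-efficacy nor the baseline outcome, and health status is not defined.

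One further rule could bring baseline values in. Under Aim 1, "we will examine all baseline outcomes and covariates to determine whether randomization has produced equivalent groups", and then "Variables exhibiting differences will be added as covariates to analyses".

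**The concern.** A mediated effect needs two paths: arm to self-efficacy, and self-efficacy to outcome. Randomisation protects the first. It does not protect the second, because nobody is randomised to a level of self-efficacy. Within each arm, people who moved and balanced better at entry are likely to report more confidence and to perform better later, whatever self-efficacy itself does. Section 4.b allows wide variation in entry function: a participant can count as at risk for disability through diabetes or BMI alone, or through difficulty walking, climbing or transferring.

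If the programme raises self-efficacy, as Hypothesis 2a predicts, this non-causal link is enough to produce a significant indirect effect. The trial could then credit self-efficacy with changing PA, physical function, cognition, functional limitations or disability when it had no part in it. The wording of the mediation question is strongly causal, so such a result would be read that way.

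**Working it through.** The plan gives no figure for the mediation analysis, so there is nothing to reproduce. The check asks how often mediation would be declared when self-efficacy has no effect on the outcome.

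**Inputs.** From the protocol (section 3): 166 per arm, N=332. Everything else is assumed:
- two-sided 5% tests, with mediation declared when both paths are significant (joint-significance test);
- programme effect on self-efficacy *a* = 0.3 or 0.5 SD, and direct programme effect on the outcome 0.2 SD;
- baseline correlation of self-efficacy with the outcome *r* = 0.2-0.5;
- visit-to-visit correlations *sM* = 0.5-0.7 (self-efficacy) and *sY* = 0.6-0.8 (outcome);
- true self-efficacy-to-outcome effect = 0.

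**Step 1: no baseline terms, confounding carried only through the measured baselines.** The spurious follow-up correlation within arm is ρ = r × sM × sY. Approximately, z_a = a√N/2 and z_b = ρ√N, and each path is significant with probability Φ(z − 1.96) + Φ(−z − 1.96). The product of the two is the false-mediation rate. In the central setting √332 = 18.22, and
- z_a = 0.3 × 18.22/2 = 2.73, giving 0.780;
- ρ = 0.4 × 0.6 × 0.7 = 0.168, z_b = 0.168 × 18.22 = 3.06, giving 0.865;
- product 0.780 × 0.865 = 0.67.

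| a | r | sM | sY | ρ | z_a | z_b | By formula | Simulated |
|---|---|---|---|---|---|---|---|---|
| 0.3 | 0.2 | 0.5 | 0.6 | 0.060 | 2.73 | 1.09 | 15% | 15% |
| 0.3 | 0.4 | 0.6 | 0.7 | 0.168 | 2.73 | 3.06 | 67% | 67% |
| 0.3 | 0.5 | 0.7 | 0.8 | 0.280 | 2.73 | 5.10 | 78% | 78-79% |
| 0.5 | 0.4 | 0.6 | 0.7 | 0.168 | 4.56 | 3.06 | 86% | 85-86% |

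**Step 2: a stable latent trait behind both variables.** The follow-up correlation is then r itself. In the mildest setting z_b = 0.2 × 18.22 = 3.64, giving 0.95, and 0.95 × 0.78 = 0.74 in place of 0.15. With a = 0.5 the rate exceeds 99%. Where a = 0.3 and r is 0.4 or more, the first path caps it at about 78%.

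**Step 3: can existing text supply the protection?** With the balance rule applied at p<0.05, the central setting moves only from 67% to 62%, because the rule looks between arms and the confounding lies between persons within arms. If the Aim 1 list is read into 2a1 and health status acts as one proxy correlated 0.5 with fitness, a latent-trait simulation (r = 0.16-0.49) still gives 49-84% at a = 0.3 and 63-100% at a = 0.5.

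**Step 4: alternatives, in the row order of the table.**

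| Model | Carried by measured baselines | Stable latent trait |
|---|---|---|
| Baseline self-efficacy and outcome in both equations | 4-6% throughout | 18, 43, 42, 48% |
| Change score on change score | 9, 20, 18, 25% | 4-6% throughout |

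Repeat runs of the adjusted trait case span 14-49%. A separate set of trait settings (r = 0.15-0.5, retest correlation 0.70 or 0.85) gave 7-20% after adjustment, and 61% in the most extreme case tried (r = 0.49, retest 0.70, a = 0.5).

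**Step 5: boundary checks.** If the programme does not change self-efficacy (a = 0), false mediation without baseline terms is about 1-6%. If a quarter were lost, as 3 of 12 were in the pilot (0.75 × 166 ≈ 124 per arm, N=248), the Step 1 range becomes 10-75%, against 4-5% adjusted. For a real path of 0.15, power after adjustment at N=332 is about 77-79%.

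**The case against.** The strongest reply is that the plan is silent, not wrong. A reader might infer that the mediation model excludes baseline values. The documents do not say that: they specify no model, and the cited procedures and M-Plus can both accommodate baseline terms or change scores. The context also leans towards baseline-referenced analysis. Mediation is introduced in connection with Hypothesis 2a, and both 2a and 2b are tested as greater improvement over time. This stands, and it is why the point is that the terms are not specified. But silence leaves the choice open until after the data are seen, between models whose false-mediation rates run from about 5% to 67% in the central setting.

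The second reply is that the 15-86% range belongs to one model, follow-up levels with no covariates, and that change scores do much better. That is correct. The range is illustrative, and change scores still give 9-25% when the measured baselines carry the confounding.

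The third reply is that the 4-6% after adjustment is built into a simulation in which the measured baselines carry everything. This also stands. A reader might infer that adding two covariates cures the problem. With a stable trait, which is what long-standing fitness most resembles, it does not.

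Finally, Hypothesis 2a1 is secondary and explanatory. The arm comparisons in Hypotheses 1, 2a and 2b are not affected by this gap, and nothing here shows that they are biased.

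**Conclusion.** The point holds as a gap in specification with a potentially large effect. Section 4.f does not specify baseline self-efficacy or the baseline outcome for the 2a1 models, and neither the Aim 1 list nor the balance rule supplies them. A follow-up-level model without them can declare mediation in about 15-86% of trials at N=332 with no self-efficacy effect present, and a stable trait can push that higher. Adjustment brings this to about 4-6% or about 14-49%, depending on whether the measured baselines or an imperfectly measured trait carry the confounding.

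Only N comes from the documents. The percentages rest on the assumed effects and correlations, on the joint-significance test, and on the programme truly raising self-efficacy. They are not a prediction for this trial. The gap covers lifestyle PA as well as the health outcomes. Baseline terms also do nothing about confounders that arise after baseline. The change is worth making, because the baseline values should already exist: section 4.e repeats the same questionnaires and tests at each visit.

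**What to change.** In section 4.f, under Hypothesis 2a1:

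1. State that every mediation model, for lifestyle PA as well as for each health outcome, includes baseline self-efficacy, the baseline value of that outcome and the Aim 1 baseline factors, in both the mediator and the outcome equation, whether or not the arms differ on them.
2. State that this reduces but may not remove confounding of the self-efficacy-to-outcome path.
3. Add a sensitivity analysis, such as a change-score model or one for unmeasured mediator-outcome confounding, to be reported before mediation is claimed. The change-score model is a useful companion because it does well where baseline adjustment does poorly, and the reverse.

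The cost is a few sentences, two more covariates per model and a little more analysis work. No new data are needed, and the only participants lost are those without a baseline value.
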